## 7.2 Registration

Registration occurs after the inclusion and exclusion criteria have been confirmed.

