## **8.0 STATISTICAL METHODS**

### **8.1 Sample Size Considerations**

This study will identify patient characteristics at the time of the baseline imaging study that are predictive of an imaging study positive for M1 in patients with CRPC and no known M1. A minimum of 2000 patients will be registered in this study. This sample size is based on the following considerations.

The primary endpoint for the study will be the occurrence of a positive imaging study for M1 at baseline (yes or no), a binary variable. All patients with a baseline imaging study will be included in the analysis of the primary endpoint. Yu et al (2012) found that 32% of 2577 men screened for a trial enrolling patients with CRPC thought to be M0 did, in fact, have M1 CRPC, and it is anticipated that this study will have a similar finding. With 1000 patients at each of the 2 possible levels of a binary variable, for a total of 2000 patients, the variable is detectable with an odds ratio of 1.312 with 80% power using a 2-sided test at alpha = 0.05, assuming an imaging study positive for M1 at baseline in 34.95% and 29.05% of patients in level 1 and level 2 of the binary variable, respectively. However, a binary variable that is distributed at a ratio of 1:5 at baseline would allow for an odds ratio of 1.422 to be detected with 80% power assuming an imaging study positive for M1 at baseline in 38.5% and 30.6% of the patients in level 1 and level 2 of the binary variable, respectively.

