### **8.2 General Considerations**

#### **8.2.1 Analysis Populations**

The all-enrolled population will include all patients registered in the study. The primary analysis will be based on the primary analysis population, which will include patients in the all-enrolled population who undergo a baseline imaging study. In addition, patients with M0 or M1 CRPC at baseline (M0 or M1 populations, respectively) will form separate analysis populations to address different questions of interest.

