### **8.3.2 Secondary Endpoints**

The proportion of patients who receive a diagnosis of M1 CRPC at the time of the baseline imaging study will be categorized as metastatic due to soft tissue (nodal and/or visceral) metastases, bone metastases, or both. The percentage of patients in each category will be computed based on the primary analysis population.

Logistic regression analyses, similar to the analyses described for the primary endpoint, will be used to identify characteristics predictive of an imaging study positive for M1 in the M0 population. Analyses will be performed using baseline information only as predictor variables with the outcome variable as a positive imaging study (yes/no) at any post-baseline time point. In addition, an analysis will be performed on the M0 population using all imaging studies collected in the study as the outcome variable (positive=yes/negative=no) with predictor variables associated with each imaging study. Appropriate methods accounting for the correlation of multiple studies for a patient, such as generalized estimating equations, will be used for this analysis. Cox regression analyses incorporating information on the time to occurrence of a positive imaging study will be performed to supplement these analyses.

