### **8.3.3 Exploratory Endpoints**

Prostate cancer treatment practice patterns will be summarized descriptively for patients with M0 CRPC and M1 CRPC. Prostate cancer interventions prior to study entry will be summarized. Additionally, the timing and sequence of prostate cancer interventions during the study will be summarized.

The identification of biomarkers in the M0 population that are predictive of an imaging study positive for M1 will be performed using logistic regression and Cox regression, as previously described. These analyses will be performed for both the primary endpoint (a positive imaging study at baseline) and the endpoint of a positive imaging study at any post-baseline time point.

The percentage of patients with CRPC with previously undiagnosed M1 at baseline will be calculated as 100 times the number of patients in the M1 analysis population divided by the total number of patients in the study.

Logistic regression analyses will be used to determine patient characteristics in the M0 population that are predictive of a positive imaging study at baseline as detected with different imaging modalities. The differing imaging modalities include MRI, 99mTc bone scintigraphy, or F-NaF PET/CT for bone imaging; and contrast-enhanced abdominal and pelvic CT or MRI for soft tissue imaging. For each imaging modality, multivariate logistic regression modeling will be used to identify factors that are independently predictive of a positive imaging study. These analyses will be performed for both the primary endpoint (a positive imaging study at baseline) and for the endpoint of a positive imaging study at any post-baseline time point.

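### The undiagnosed-M1 percentage in Section 8.3.3 counts any registered man without a baseline scan as M1-free; it should use the imaged population the plan already defines

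*Combined protocol and SAP*

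**What the plan says.** Describing the percentage of patients with undiagnosed M1 at baseline is an exploratory objective (protocol Section 3.3). Section 8.3.3 gives its formula: "100 times the number of patients in the M1 analysis population divided by the total number of patients in the study".

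Section 8.2.1 defines the populations that bear on it:

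- All-enrolled: "The all-enrolled population will include all patients registered in the study".
- Primary analysis: "patients in the all-enrolled population who undergo a baseline imaging study".
- By baseline status: "patients with M0 or M1 CRPC at baseline (M0 or M1 populations, respectively) will form separate analysis populations".

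Section 7.2 sets the trigger for registration: "Registration occurs after the inclusion and exclusion criteria have been confirmed". None of the criteria in Sections 5.1 and 5.2 is a completed baseline scan.

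Section 8.3.2 divides the men found to have M1 at baseline into soft tissue, bone or both, and there the denominator is explicit: "The percentage of patients in each category will be computed based on the primary analysis population". Section 8.1 restricts the primary endpoint in the same way: "All patients with a baseline imaging study will be included in the analysis of the primary endpoint".

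The closing note of the combined document states that the SAP was not finalized, so no later text defines the Section 8.3.3 denominator.

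**The concern.** M1 status is established by imaging findings (Section 7.6.15). A registered man who is never scanned at baseline therefore cannot belong to the M1 population. If the denominator is all registered men, he still counts there, and the formula treats him as though he had been scanned and found negative.

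Section 8.2.1 distinguishes registered men from imaged men, so the plan allows for the two groups to differ. It names a population that leaves out the un-imaged, but Section 8.3.3 does not use it.

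Two things are at stake. The first is the study's own description of how often M1 disease goes unrecognized, the issue that Section 1.2 uses to motivate the study. The second is internal consistency: the overall M1 percentage and its breakdown by site count the same men but may be divided by different totals.

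**Working it through.** **Figures in the plan.** The plan states no result for this percentage, so there is none to reproduce. The relevant number is the 32% anticipated in Section 8.1. The rates used for sample size are consistent with it: the equal split gives (34.95 + 29.05)/2 = 32.0%, and the 1:5 split gives (38.5 + 5 × 30.6)/6 = 31.9%. The stated 80% power with 1000 men per level also reproduces (80.8% by the pooled two-proportion formula). That calculation does not use the Section 8.3.3 formula.

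**Inputs.**

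- N = 2000 registered (Section 8.1: "A minimum of 2000 patients will be registered in this study").
- p = 32%, taken as the M1 percentage among imaged men.
- u = fraction of registered men without a baseline scan. The documents give no value; the values below are assumptions.

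**Formulas.** Imaged men number N(1 - u), of whom pN(1 - u) are M1.

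- Section 8.3.3, denominator read as all registered: pN(1 - u)/N = p(1 - u).
- Primary analysis population as denominator: pN(1 - u)/[N(1 - u)] = p.
- Shortfall: p × u in percentage points, which is a relative reduction of u.

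| Assumed u | Imaged | M1 | Section 8.3.3 formula | Imaged denominator | Shortfall (points) |
|---|---|---|---|---|---|
| 0% | 2000 | 640 | 32.0% | 32.0% | 0 |
| 2% | 1960 | 627.2 | 31.4% | 32.0% | 0.6 |
| 5% | 1900 | 608 | 30.4% | 32.0% | 1.6 |
| 10% | 1800 | 576 | 28.8% | 32.0% | 3.2 |

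**Agreement with Section 8.3.2.** The three site categories are mutually exclusive and together cover all M1 men, so on the imaged denominator they sum to p. At u = 10% they sum to 576/1800 = 32.0%, while Section 8.3.3 gives 576/2000 = 28.8%. The two agree only at u = 0 (or if no man is M1).

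**Scale against sampling error.** The 95% half-width at 32% and n = 2000 is 1.96 × √(0.32 × 0.68/2000) = 2.04 points. The shortfall 32 × u passes this when u exceeds about 2.04/32 = 6.4%.

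**What the figure means for all registered men.** Let q be the M1 percentage among un-imaged men. The percentage among all registered men is p(1 - u) + qu. At u = 10% this is 28.8% if q = 0, 30.8% if q = 20%, 32.0% if q = 32%, 33.8% if q = 50%, and (576 + 200)/2000 = 38.8% if q = 100%. Taking scan results as correct, the Section 8.3.3 formula always gives the lowest value in this range. The imaged denominator gives the right value for all registered men only when q = p.

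**The case against.** The strongest reply is that u may be zero or close to it. Bone and soft tissue imaging is a required baseline assessment (Section 7.1, Table 1). Section 4.0 assigns men to the M0 or M1 Phase by the baseline imaging result, describes no route for a man without one, and speaks of M1 being diagnosed at registration. This stands: the shortfall is conditional. A reader might infer that the estimate is certain to be biased downward, or that the site percentages are certain not to add up. The documents support neither without a value of u above zero. They do allow such a value, because registration does not wait for the scan and Section 8.2.1 separates the two groups.

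The denominator wording is also not a defined term, so imaged men could have been meant. The closest defined group is the all-enrolled population, and naming the denominator settles the matter on either reading.

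A reader might take the un-imaged fraction as the bias in percentage points. It is the relative reduction: 10% un-imaged costs 3.2 points, not 10. Nor is the imaged percentage automatically the truth for all registered men; that needs missing imaging to be unrelated to M1 status.

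A reader might also infer that the plan tests this percentage against the cited 32%. Section 1.2 gives that figure as background, and Section 8.1 uses it for planning. Section 8.2.3 permits descriptive comparison with external data in general terms but does not name this percentage. The 32% is described as a share of men screened, and the documents do not show whether all of them were imaged.

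Finally, the summaries in Sections 8.5 and 8.6 should supply the counts needed to recompute the percentage. That reduces the harm but does not correct the stated formula. One limit remains after the change: Section 8.2.1 does not say whether a scan of bone alone or of soft tissue alone qualifies as a baseline imaging study.

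**Conclusion.** The point holds conditionally. Read in its most natural sense, the Section 8.3.3 formula returns the M1 percentage among imaged men multiplied by (1 - u). At 32% this is a shortfall of 0.6, 1.6 and 3.2 points for assumed u of 2%, 5% and 10%, and none if every registered man is scanned. For u of 5% or less the shortfall lies within the roughly 2.0-point half-width of the estimate. Whenever u is above zero and any man is M1, the figure also fails to match the sum of the Section 8.3.2 percentages.

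The conclusion rests on reading the denominator as all registered patients and on some of them lacking a baseline scan. A reader might infer that the study's main results are at risk. They are not: the primary endpoint and the site percentages already use imaged men, the sample size calculation does not involve this formula, and the affected percentage is exploratory and descriptive. This is a minor correction.

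**What to change.** In Section 8.3.3, replace the denominator with the number of patients in the primary analysis population, as already defined in Section 8.2.1. Beside the percentage, report how many men were registered but not imaged at baseline. Add one sentence saying that the estimate describes imaged men and extends to all registered men only if missing imaging is unrelated to M1 status.

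The Section 8.3.2 site percentages will then sum to the Section 8.3.3 figure, apart from rounding. The cost is one changed phrase, one reported count and one sentence of interpretation. No new data are needed, and no other analysis changes.

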### Baseline

The patient population consists of patients with CRPC and no known M1. The patient will undergo the baseline visit  $\leq$  28 days after written informed consent is obtained. Baseline assessments will include demographics and medical history; date of diagnosis with CRPC, with confirming serum PSA values and associated hormonal therapy; prostate cancer imaging study history; Eastern Cooperative Oncology Group (ECOG) performance status; height and weight; Adult Comorbidity Evaluation-27 (ACE-27); Gleason score; serum PSA history; current opioid analgesic use (yes/no); concomitant medications; pain status (with Brief Pain Inventory [BPI]); documentation of prior and ongoing prostate cancer interventions; and imaging studies (bone and soft tissue) to determine M1 disease status. In addition, blood samples will be collected for clinical laboratory tests (alkaline phosphatase, hemoglobin,

lactate dehydrogenase [LDH], serum albumin, serum PSA, and testosterone), and for AOR, if patient provides consent, for biomarkers potentially predictive of treatment effects, or prognostic for MFS, OS, or an imaging study positive for metastatic disease.

Patients who have undergone an imaging study to determine the presence of M1 (bone and/or soft tissue)  $\leq$  3 months prior to signing the ICF are ineligible. However, these patients may enter the study  $>$  3 months after their last imaging study if at that time they meet all eligibility criteria. Patients who are deemed eligible on the basis of inclusion/exclusion criteria will be registered in the trial and receive a unique identifier at that time.

Patients with baseline imaging studies confirming M0 CRPC will be entered into the M0 Phase. Patients with a baseline imaging study indicating previously unknown M1 CRPC will be entered into the M1 Phase.

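### Section 8.3.3 runs the baseline-positivity biomarker and modality regressions in the M0 population, which by definition contains no baseline positives

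*Combined protocol and SAP*

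**What the plan says.** Section 8.3.3 contains two regression analyses tied to the M0 population.

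- **Biomarkers.** "The identification of biomarkers in the M0 population that are predictive of an imaging study positive for M1 will be performed using logistic regression". The full method is stated as follows: the work "will be performed using logistic regression and Cox regression, as previously described".
- **Imaging modality.** "Logistic regression analyses will be used to determine patient characteristics in the M0 population that are predictive of a positive imaging study at baseline", split by modality. It continues: "For each imaging modality, multivariate logistic regression modeling will be used to identify factors that are independently predictive of a positive imaging study". Only logistic regression is named here.

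Each paragraph ends by naming two outcomes. It says "These analyses will be performed for both the primary endpoint (a positive imaging study at baseline") and then adds a positive study at any later time.

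The populations are set in Section 8.2.1: "patients with M0 or M1 CRPC at baseline (M0 or M1 populations, respectively) will form separate analysis populations". Section 4.0, under Baseline, gives the routing: "Patients with a baseline imaging study indicating previously unknown M1 CRPC will be entered into the M1 Phase". Section 7.6.15 sets the threshold for M1: an unequivocal bone lesion, a regional or distant node of at least 2 cm, or a visceral metastasis.

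The Cox regression described before 8.3.3 is in Section 8.3.2, for patients who were M0 at baseline: "Cox regression analyses incorporating information on the time to occurrence of a positive imaging study will be performed to supplement these analyses".

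The last page of the combined document records that the SAP was never finalized because data were insufficient.

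**The concern.** The population is selected on the outcome. A patient belongs to the M0 population because his baseline imaging did not show M1, and the model then asks which characteristics predict that his baseline imaging showed M1. The answer is no for every patient, so there is nothing to regress.

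Two objectives in Section 3.3 depend on these models: biomarkers of a positive baseline study, and predictors of a positive baseline study by modality. As written, neither has an analysis that can be run. Whoever does the analysis would have to replace the stated population, and settle the role of Cox regression, without a prespecified rule.

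**Working it through.** **1. The planning figures, reproduced.** Section 8.1 expects a baseline M1 rate of 32% and gives 80% power with 1000 patients at each level of a binary variable, at rates of 34.95% and 29.05%.

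- Mean rate: (34.95% + 29.05%) / 2 = 32.00%, which agrees with the planning rate.
- Odds ratio: (0.3495 / 0.6505) / (0.2905 / 0.7095) = 1.312, as stated.
- Standard error under the null: √(2 × 0.32 × 0.68 / 1000) = 0.02086. Under the alternative: √((0.3495 × 0.6505 + 0.2905 × 0.7095) / 1000) = 0.02082.
- Power: Φ[(0.0590 − 1.96 × 0.02086) / 0.02082] = Φ(0.870) = 0.808, which reproduces the stated 80%.

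These figures belong to the primary endpoint in all imaged patients and are not in dispute. They supply the 32% used below.

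**2. Event counts by population**, taking 2000 registered and all imaged at baseline.

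| Population | Patients | Positive at baseline |
|---|---|---|
| Primary analysis population | 2000 | 0.32 × 2000 = 640 |
| M0 population | 0.68 × 2000 = 1360 | 0 by definition |

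If the baseline rate were 20% to 40% (an assumed range), the primary analysis population would hold 400 to 800 positives and M0 would hold 1600 to 1200 patients. The M0 event count stays at 0.

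**3. What a logistic model does with no events.** With every outcome equal to 0 the log-likelihood is −Σ log(1 + exp(ηᵢ)), where ηᵢ is the linear predictor. It rises towards 0 as the intercept goes to minus infinity, so no finite maximum exists. A trial fit to 1360 zero outcomes with one simulated binary predictor behaved accordingly:

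| Iteration limit | Intercept | Standard error of slope |
|---|---|---|
| 10 | −11.6 | 10.7 |
| 25 | −26.6 | 19,316 |
| 50 | −27.6 | 31,847 |

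The slope stayed at zero to within rounding and carried no information.

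**4. The objectives and the primary endpoint.** In Section 3.3 the biomarker and modality objectives come in pairs. The future-imaging member of each pair is limited to patients who were M0 at baseline; the baseline member is not. Section 8.3.1 analyses the same baseline endpoint in everyone who had a baseline imaging study. Section 8.3.3 conflicts with both.

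**5. Whether M0 could carry a looser meaning.** The rest of 8.3.3 does not support one. The percentage with undiagnosed M1 at baseline takes the M1 analysis population as its numerator, so the section itself counts baseline positives as M1. The metastasis-free survival paragraph uses the M0 population and admits only patients confirmed as M0 at entry.

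**6. Cox regression.** The Cox analysis in 8.3.2 models time to a positive study. For M0 patients, metastasis-free survival is timed from the baseline imaging date. Status on that scan is known at time zero and contributes no follow-up, so Cox regression cannot be applied to it in any population.

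**The case against.** The best defence is that this is a drafting slip with one evident correction. Section 8.3.3 creates no new endpoint: it names the primary endpoint, whose population 8.3.1 fixes as all imaged patients, and the matching objectives carry no M0 limit. A statistician would see the failure on the first run and could infer the intended population. This stands, and it sets the severity. It does not remove the point, because the restriction appears in two separate paragraphs and no finalized SAP overrides it.

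On Cox, the phrase in "will be performed using logistic regression and Cox regression, as previously described" can be read as carrying over the earlier arrangement: logistic regression for baseline status, logistic and Cox for later positivity. That reading is reasonable. The sentence that follows applies the analyses to both outcomes without distinction, so the text needs clarifying, but this is a secondary wording point.

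The modality wording might seem to rescue the M0 restriction if a patient could be positive on one modality and still be M0. Under 7.6.15 a qualifying finding makes the patient M1. An equivocal bone scan is sent for more sensitive imaging to settle M1 status. The documents do not say how a first scan later cleared would be coded for its own modality, so the certain statement is that patient-level baseline positivity is zero in M0. Nothing in 8.3.3 suggests that cleared equivocal scans were the intended outcome.

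A reader might also infer that the primary analysis or the sample size is compromised. The documents do not support that: 8.3.1 and 8.1 use all imaged patients, and the power figure reproduces. Nor does 3.3 reserve M0 for future imaging alone, since treatment patterns and metastasis-free survival are also limited to M0. The contrast holds only within the biomarker and modality pairs.

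**Conclusion.** The point holds as a conflict between population and outcome. The baseline half of the biomarker analysis and of the modality analysis cannot be estimated as written: 0 events in about 1360 M0 patients, where the primary analysis population would offer about 640 in 2000. The zero follows from the definitions and needs no assumption. The 1360 and 640 assume full accrual, baseline imaging in every patient and the 32% planning rate. Actual numbers may be much smaller, given the recorded reason for not finalizing the SAP. The biomarker models would use only those who consent to the additional optional research, a share the documents do not give.

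Severity is minor. The analyses are exploratory, the failure would be visible rather than yield a misleading estimate, and the primary and secondary analyses are untouched. The finding says nothing either way about the merits of the post-baseline models, which rest on imaging done at the investigator's discretion; it says only that the M0 population does not contradict that outcome.

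**What to change.** In Section 8.3.3, or in an SAP if one is written:

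1. Fit the baseline-positivity models in the primary analysis population. Limit the biomarker models to patients who consented to the optional research samples, and each modality model to patients imaged at baseline with that modality.
2. Use logistic regression only for the baseline outcome.
3. Keep the M0 population for the post-baseline outcome only, with logistic and Cox regression for biomarkers and logistic regression for modality.

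The cost is a few changed sentences. No visits, patients or samples are added, and dropping Cox regression for the baseline outcome loses nothing.

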### **Safety Measures:**

The collection of adverse events (AE) will be limited to SAEs in patients who receive at least 1 partial ( $> 0$  mL) infusion of Provenge® (sipuleucel-T) during the study and that occur at any

time from the first infusion through 30 days after the last infusion, regardless of relationship to Provenge.

Any patient who is not diagnosed with M1 CRPC and receives at least 1 partial ( $> 0$  mL) infusion of Provenge during the study will be withdrawn from the study. Serious adverse events that occur in such patients will be recorded as described above.

For patients who withdraw consent or are determined to be lost to follow-up, the investigator will use the National Death Index (NDI) or Social Security Death Index (SSDI) to ascertain any deaths not reported in the study. The date of death, when available, will be recorded.

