### **5.3 Removal of Patients from the Study**

Whenever possible, patients should remain in the study and continue with protocol-specified assessments. A patient may be withdrawn from the study if, in the investigator's clinical judgment, it is in the best interests of the patient.

Patients may discontinue their participation in the study at any time without prejudice toward their future medical care. A patient may choose to discontinue all evaluations and participation (including survival follow-up), or may discontinue all study evaluations with the exception of being followed for survival. If a patient chooses to withdraw from the study, the investigator should make every reasonable attempt to confirm the status of all ongoing SAEs meeting the criteria defined in Section 7.6.18. The date and reason for withdrawal will be recorded in the source documentation and on the eCRF.

If a patient fails to respond to requests for follow-up, the study site will (at a minimum) send a registered letter to the patient requesting contact. All attempts to resume contact (including copies of written correspondence) will be included in the source documentation. Patients who do not respond to requests for follow-up after all reasonable attempts to establish contact will be considered lost to follow-up. Data on all patients who withdraw consent or are determined to be lost to follow-up will be reviewed by the investigator through the National Death Index (NDI) or Social Security Death Index (SSDI) to ascertain any deaths not reported in the study. The date of death, when available, will be gathered from the NDI or SSDI and recorded on the eCRF.

Any patient who is not diagnosed with M1 CRPC and receives at least 1 partial ( $> 0$  mL) infusion of Provenge during the study will be withdrawn from the study. Serious adverse events that occur in such patients will be recorded as described in Section 7.6.18.

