### **7.6.14 Survival Status**

Survival status is assessed in patients at all M0 and M1 data collection time points. The terms “alive” with the date of confirmation, “deceased”, or “unconfirmed” are collected. For those patients recorded as “deceased”, an additional eCRF page entitled “Date and Cause of Death” will become available. On this page, “Date of death” and “Cause of Death (check all that apply): Disease progression, Cardiac event, New primary cancer, Cerebrovascular event, and other (specify)”, are listed as choices.

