Metastasis-free survival will be defined as time from the date of the baseline imaging study to the first occurrence of M1 or death due to any cause in the M0 population. Patients who are not observed to develop M1 or who do not die will be censored at the last time observed for determination of M1. Only patients who are confirmed with M0 CRPC at study entry will be included in the analysis. Cox regression analyses will be used to analyze the MFS endpoint. Univariate Cox regression analyses will be performed separately for each baseline variable of interest. A multivariate Cox regression analysis will be performed including all baseline variables of interest. Various model selection procedures will be investigated, including forward, backward, and stepwise regression to identify a model that includes explanatory factors that are independently predictive of development of M1 or death. Supplementary analyses, including time-varying covariates of ECOG performance status and laboratory parameters, will also be provided.

Overall survival will be defined as the time from diagnosis with M1 CRPC until death. Patients who do not die will be censored at the last date they were known to be alive. Analyses similar to those described for MFS will be performed in the M1 population to determine patient characteristics that can be used to predict OS. The Kaplan-Meier method will be used to quantify the survival duration from the time of diagnosis with M1 CRPC. In addition, the effect of prostate cancer interventions and their sequencing on OS will be evaluated using a Cox regression analysis with time-varying covariates.

The timing and sequence of prostate cancer interventions will be summarized descriptively for the M1 population. The time to prostate cancer interventions will be defined as the time from the date of diagnosis with M1 CRPC until initiation of the prostate cancer intervention.

Changes in serum PSA levels during treatment for M1 CRPC will be summarized descriptively for the M1 population. For treatments with sufficient patient numbers, changes in serum PSA levels over time, PSA progression, and PSA progression-free survival will be

summarized descriptively by treatment. The maximum percentage reduction in serum PSA levels will also be summarized descriptively by treatment.

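### Exploratory OS: deaths found in a death index after loss count as events, but lost patients with no death found are censored at last contact, so censoring depends on the outcome

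*Combined protocol and SAP*

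**What the plan says.** Section 8.3.3 gives the OS rules: "Overall survival will be defined as the time from diagnosis with M1 CRPC until death", and "Patients who do not die will be censored at the last date they were known to be alive". Deaths learned of only through an index are not excluded. The estimator for duration is named: "The Kaplan-Meier method will be used to quantify the survival duration from the time of diagnosis with M1 CRPC". Cox models are to be used for predictors of OS and for intervention sequencing.

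Section 5.3 adds a second source of deaths: "Data on all patients who withdraw consent or are determined to be lost to follow-up will be reviewed by the investigator", the purpose being "to ascertain any deaths not reported in the study". What the search leaves behind is a death date only: "The date of death, when available, will be gathered from the NDI or SSDI and recorded on the eCRF". The synopsis repeats the duty under Safety Measures: "For patients who withdraw consent or are determined to be lost to follow-up, the investigator will use the National Death Index" or its Social Security counterpart.

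The date a patient was last known alive comes from study contact. Section 7.6.14 says "Survival status is assessed in patients at all M0 and M1 data collection time points", and an entry of alive carries its own confirmation date.

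No section states when the index is searched, whether the search is repeated, through what date it is complete, or how a lost patient with no index death is handled in OS. The closing note of the combined document says the SAP was never finalized, so no later text settles this.

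**The concern.** After loss, the search goes on finding deaths, but survivors stop contributing time at risk. A lost patient who dies and is found in the index is followed to death. A lost patient who lives, or whose death the index misses, is removed at last contact. Beyond the point of loss the only lost patients still in the risk set are those who will be recorded as dying.

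Kaplan-Meier and Cox analyses require censoring that carries no information about the later event. Here it does so by construction, even if loss itself is unrelated to prognosis.

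Two outputs are exposed. One is survival from M1 diagnosis, which the protocol lists as something to quantify. The other is the set of OS predictors, where a factor associated with loss could look associated with death.

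**Working it through.** **The plan's own figures.** OS has no sample size, event count or loss rate. The only sizing is for the primary endpoint (section 8.1), and it reproduces: OR = (0.3495/0.6505)/(0.2905/0.7095) = 1.312, with power 0.81 at 1000 per level. Section 8.1 expects about 32% M1 at baseline, so the baseline M1 population is about 0.32 × 2000 = 640.

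**Inputs**
- From section 4.0: 2 years of accrual plus 5 years, so potential follow-up C is 5 to 7 years for patients with M1 at baseline.
- Assumed, because not stated: exponential survival with a 3-year median (λ = ln 2/3 = 0.231 per year), uniform accrual, annual loss rate μ, complete index searched to cut-off, loss unrelated to prognosis.

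**Formula.** Among patients alive at time t, the rule drops those already lost who will survive to cut-off. Let p(t) = 1 − exp(−μt) be the share lost, and s(t) the average of exp(−λ(C − t)) over C. All deaths are still counted, so

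apparent hazard / true hazard = 1 / [1 − p(t)·s(t)].

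At μ = 0.10:
- t = 3: p = 0.259, s = 0.504, ratio = 1/(1 − 0.131) = 1.15.
- t = 5: p = 0.393, s = 0.801, ratio = 1/(1 − 0.315) = 1.46.

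Integrating the apparent hazard from 0 to 5 years gives the 5-year OS that Kaplan-Meier would report. Simulations of the same setting differ in how the percentage becomes a rate and how loss is dated.

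| Annual loss | 5-year OS, formula | 5-year OS, simulations | Median, formula |
|---|---|---|---|
| none (truth) | 31.5% | 31.5% | 3.00 y |
| 2% | 30.5% | 30.4% | 2.96 y |
| 5% | 29.0% | 28.7–29.0% | 2.92 y |
| 10% | 26.6% | 26.0–26.6% | 2.84 y |
| 15% | 24.3% | 23.3–24.3% | 2.78 y |

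**Search timing.** At 10% annual loss, one search 6 months after loss cuts the 5-year deficit from about 5 points to 1.7, and one at 12 months to 2.9. With loss dated back to the last six-monthly contact the reductions are smaller: about half and about a third. The median shift does not shrink.

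**Factor with no effect on death** (index complete to cut-off). Annual loss of 10% v 5% gives a hazard ratio of 1.06–1.07, 10% v 3% gives 1.09–1.10, and 15% v 5% gives 1.13. The last falls to 1.06 or 1.08 with a single search at 6 or 12 months. With 640 patients and medians of 24 to 36 months, a nominal 5% test rejects in 5–7% of trials when loss by two years is 5% v 10%, and in 14–26% when it is 5% v 20%. With equal loss there is no such effect.

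**Checking the remedy.** Censoring patients with no index death at the coverage date restores 31.5% when the index is complete. With a 90% complete index, a 36-month median and 20% lost by two years, the written rule gives 26.0% and the remedy 32.9%, against a true 31.4%.

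Next, let sicker patients be lost more often (frailty SD 1 on both death and loss, 10% annual loss, true 5-year OS 34.5%):

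| Index completeness | Written rule | Coverage-date censoring | Last contact, later index deaths ignored |
|---|---|---|---|
| 90% | 32.1% | 35.9% | 39.0% |
| 70% | 33.5% | 38.7% | 39.0% |
| 50% | 34.9% | 41.6% | 39.1% |

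In all three rows both alternatives lie above the truth. At 50% the written rule also errs slightly upward. With a complete index in a similar setting (20% lost by two years, true 24.6%), coverage-date censoring is exact at 24.6%, the written rule gives 22.4% and last-contact censoring 29.0%.

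**The case against.** The strongest reply has four parts.

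1. **Low stakes.** OS is exploratory, section 8.2.2 says no formal hypotheses are tested, and censoring conventions would normally be settled in an SAP that was never completed. This stands as a limit on importance. But the rules as written already determine a biased estimate, so this is more than missing detail.

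2. **Loss may be small.** Section 7.5 allows chart review and calls to the patient or physician, and section 5.3 requires a registered letter. At 2% annual loss the 5-year error is about 1 point. This stands: the loss rates above are assumptions.

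3. **The direction is not guaranteed.** A reader might infer that OS is necessarily understated and that predictors will show false hazard ratios. The documents do not support that. They give no index completeness, no search date and no sign that loss differs by any factor, and section 5.3 itself expects some death dates to be unavailable.

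4. **The remedy can do worse.** With a 70% or 50% complete index and loss related to prognosis, the written rule is closer to the truth than either alternative. This stands, so the two analyses cannot be presented as bracketing the true value.

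One could also read the last date known alive as including a clear index search. Section 7.6.14 ties that date to confirmation at data collection, and section 5.3 records only deaths, so the text does not say this.

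**Conclusion.** The defect is real and confined to exploratory OS. Sections 5.3, 7.6.14 and 8.3.3 together make censoring depend on the outcome, and nothing in the documents repairs it.

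With a reasonably complete index the bias is downward. Under the assumptions in the working, 5-year OS is about 1, 3 and 5 to 6 points low at 2%, 5% and 10% annual loss, and the median about 0.05 to 0.2 years low. A single early search reduces the 5-year error. Many missed deaths combined with greater loss of sicker patients can weaken or reverse it. A false hazard ratio needs loss to differ by the factor.

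Two further inferences should be resisted. The primary endpoint and the 2000-patient sample size are untouched, because they rest on baseline imaging. And the OS remedy does not carry over to MFS: a death index says nothing about metastasis, so moving MFS censoring to the coverage date would treat unimaged lost patients as metastasis-free.

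**What to change.** In section 8.3.3 (and in any SAP):

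- Record the date of each index search and the date through which the index is complete. Censor lost or withdrawn patients with no death found at that coverage date, capped at study cut-off.
- As a sensitivity analysis, censor all such patients at last contact and ignore deaths found only afterwards. This is unbiased if loss is unrelated to prognosis, but overstates survival if sicker patients are lost more often.
- Report how many were lost, by the main predictors, and how many of their deaths came only from the index.
- For MFS, keep censoring at the last M1 assessment. At least in a sensitivity analysis, do not count deaths found only through the index after loss.

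The cost is a few sentences, the recorded dates and one extra run. The downside is that deaths the index misses count as survival time, and the sensitivity analysis does not necessarily bracket the truth when loss is related to prognosis. The report should say so.
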